10.1. Statistical Hypothesis

Let μ_0 and μ_1 be the population means of the percent change from baseline in calculated LDL-C at week 24 under placebo and evinacumab, respectively. The following null hypothesis and alternative will be tested:

$$\begin{aligned} H_0 : \mu_0 &= \mu_1 \\ &\text{versus} \\ H_1 : \mu_0 &\neq \mu_1 \end{aligned}$$

LDL-apheresis treatment (Yes/No), and geographical region (Japan, Rest of World) will be the 2 stratification factors for patient randomization, and will be accounted for in the statistical modeling for efficacy.

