Continuous secondary efficacy endpoints defined in Section 4.2.2 and Section 4.2.3 anticipated to have a non-normal distribution (ie, TG and Lp[a]), will be analyzed using a robust regression model (ie, ROBUSTREG SAS procedure with M-estimation option) with treatment group and randomization stratum as main effect and corresponding baseline value(s) as a covariate. Missing values will be addressed using a multiple imputation approach, which will be described in the SAP. The variables in the multiple imputation model will at least include the same variables as used in the robust regression model. The treatment group combined means will be provided with respective SE estimates. The combined mean difference between the treatment groups will be provided with the SE, 95% confidence interval (CI) and p-value.

III. Binary endpoints

Binary secondary efficacy endpoints defined in Section 4.2.2 and Section 4.2.3 will be analyzed using stratified logistic regression (using the strata option of the SAS logistic procedure) with treatment group and randomization stratum as main effect and corresponding baseline value(s) as a covariate. Missing values will be addressed using a multiple imputation approach, which will be described in the SAP. The variables in the multiple imputation model will at least include the same variables as used in the logistic regression model. Treatment effects will be compared and the combined odds ratio estimate between the treatment groups, with their corresponding 95% CI and p-value will be provided.

In the data dependent case that the logistic regression method is not applicable (eg, the response rate is zero in one treatment arm and thus the maximum likelihood estimate may not exist), the last observation carried forward (LOCF) approach would be used for handling of missing values and an exact conditional logistic regression would be performed to compare treatment effects. The LOCF imputation method will consist of using the last value obtained up to the week 24 time window to impute the missing week 24 value.

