2. INVESTIGATION PLAN

2.1. Study Design and Randomization

This is a randomized, double-blind, placebo-controlled, parallel-group study to evaluate the efficacy and safety of evinacumab in patients with homozygous familial hypercholesterolemia (HoFH).

Patients who meet all the inclusion criteria and none of the exclusion criteria will be randomized in a 2:1 ratio to receive evinacumab 15 mg/kg IV every 4 weeks (Q4W) or matching placebo IV Q4W for the 24-week double-blind treatment period (DBTP). The randomization will be stratified by apheresis treatment (Yes, No) and by region (Japan, Rest of World). After completion of the DBTP, all patients will enter a 24-week open-label treatment period (OLTP) and receive open-label evinacumab 15 mg/kg IV Q4W.

After completion of the 24-week OLTP, all patients who have successfully completed this study may have the opportunity to participate in a separate open-label (OL) study. All patients that enroll in the separate OL study will continue to receive open-label evinacumab at a dose of 15 mg/kg IV Q4W. Those patients who do not participate in the separate open-label study will undergo a 24-week follow-up after the last dose of study treatment.

The analyses will be conducted in 2 steps. The first analysis will be conducted as soon as all patients have been randomized and all data through week 24 (double-blind treatment period) has been collected and validated; this first analysis will consist of the final analysis of the double-blind primary and secondary efficacy endpoints. The safety analysis will be performed on all safety data collected and validated at the time of the first step analysis database lock. Since the double-blind primary efficacy measure data collection will have been concluded at the time of this first analysis, the significance level for the study remains at 0.05.

The second analysis will be performed with the data from the open-label treatment period and will consist of the final analysis for the safety and efficacy measures beyond week 24-time point.

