5.7.2.2. Continuous Endpoints Anticipated to have a Non-normal Distribution

Continuous secondary efficacy variables defined in Section 4.7.2 and 4.7.3 anticipated to have a non-normal distribution (i.e. TG and Lp(a)) will be analyzed using the multiple imputation approach for handling of missing values as described in Appendix 10.7, with data log-transformed before imputation process and then back transformed to create the imputed data sets using the TRANSFORM statement of SAS MI procedure.

The percent change from baseline at time point of interest will be derived from observed and imputed lipid values at this time point. Multiple imputation will be followed by robust regression model (Mehrotra 2012) to compare treatment group differences, with the endpoint of interest as the response variable using M-estimation (using SAS ROBUSTREG procedure) with treatment group, randomization strata (as per IVRS/IWRS) and corresponding baseline value(s). Combined means estimates for both treatment groups, as well as the differences of these estimates, with their corresponding SEs, 95% CIs and p-value will be provided through the SAS MIANALYZE procedure.

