5.7.2.3. Binary Endpoint Variables

Binary secondary efficacy endpoints defined in Section 4.7.2 and 4.7.3 will be analyzed using the multiple imputation approach for handling of missing values as described in Appendix 10.7.

The binary endpoint at time point of interest will be derived from observed and imputed lipid values at this time point. Multiple imputation will be followed by stratified logistic regression,

(with strata defined as randomized in the IVRS/IWRS) using the strata option of the SAS logistic procedure. The logistic regression procedure will be used to compare treatment group differences, with the model containing treatment group and corresponding baseline value(s) as covariate, stratified by randomization strata defined as per IVRS/IWRS. Combined estimates of odds ratio versus placebo, 95% CI, and p-value will be obtained through the SAS MIANALYZE procedure.

In the data dependent case such logistic regression is not applicable (e.g. the response rate is zero in one treatment arm and thus the maximum likelihood estimate may not exist), the last observation carried forward (LOCF) approach would be used for handling of missing values. Treatment effects would be compared using the stratified exact conditional logistic regression method, specifically using the strata option of the SAS logistic procedure (with strata defined as randomized in the IVRS/IWRS). In case the model would not converge with stratification variables, an unstratified exact logistic regression will be performed. The LOCF imputation method will consist of using the last value obtained up to the week 24 efficacy analysis window to impute the missing week 24 value.

In case of computing issues with exact logistic regression, the baseline level(s) will be entered in the model as a categorical variable(s) using quartiles. Exact odds ratio versus placebo, 95% CI, and p-value will be provided.

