10.7. Detailed Description of the Multiple Imputation Procedure

The following is a detailed description of the multiple imputation procedure which will be used for analysis of the secondary efficacy endpoints.

In general, the missing pattern is anticipated to be not monotone, a two-step approach will be used:

- Step 1: the MCMC method will be used in conjunction with the IMPUTE=MONOTONE option to create an imputed data set with a monotone missing pattern. Set the SEED=1629 option in SAS MI procedure.
- Step 2: Using the monotone data set from step 1, missing data will be imputed using the regression method. Set the SEED=9261 option in SAS MI procedure.

The imputation model for step 1 will include the treatment group and the values of the analyzed parameter at baseline and planned time-points up to week 24.

The imputation model for step 2 will include the same variables as in step 1 with the following additional variables:

- the randomization strata (apheresis treatment status strata);
- age, BMI, and gender (age and BMI included as continuous variables).

Non-continuous variables included in the imputer's model (i.e., treatment group, randomization strata and gender) are not expected to be missing.

In addition, for continuous efficacy variables anticipated to have a non-normal distribution (i.e. TG and Lp(a)), data will be log-transformed before imputation process and then back-transformed to create the imputed data sets using the TRANSFORM statement of SAS MI procedure.

For variables other than those continuous efficacy variables anticipated to have a non-normal distribution (i.e. TG and Lp(a)), for each simulation leading to negative imputed value, another value will be redrawn using MINIMUM option of SAS MI procedure.

The number of imputations (100) will be informally verified by replicating sets of 100 imputations and checking whether the combined results are stable. If not stable, the number of imputations will be increased and informally checked as above, and thus continued until stable estimates are obtained.

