Imputation of missing data during the on-treatment period

Missing LDL-C values during the on-treatment period will be imputed from other on-treatment measurements assuming Missing At Random, using SAS® MI procedure.

Only LDL-C values collected during the on-treatment period will be included in the imputation model. This way, missing LDL-C values during the on-treatment period will be imputed based solely on observed on-treatment LDL-C values.

The imputation model will include the treatment arm, baseline LDL-C value, and all LDL-C values at pre-specified visits. Since the pattern of missing data will necessarily be non-monotone, a Monte-Carlo Markov Chain (MCMC) method will be used. A minimum value of 0 will be specified in order to avoid negative imputed LDL-C values.

A sample SAS code is provided below:

```
proc mi data=DATAIN out=DATAOUT nimpute=100 minimum=. 0 0 0 0 0 0 0 0 seed=1629;  
  mcmc impute=monotone;  
  var ARM LDL_BASE LDL_W2 LDL_W4 LDL_W8 LDL_W12 LDL_W16 LDL_W20  
  LDL_W24;  
run;
```

As stated above, the input dataset DATAIN will include only LDL-C values collected during the on-treatment period. Any LDL-C values collected during the post-treatment period will be excluded from the input dataset. In practice, the MI procedure will generate imputed values for all missing values (whether on-treatment or post-treatment), but only imputed values during the on-treatment period will be kept in the final datasets that will be analyzed using ANCOVA. Imputed values during the post-treatment period will be discarded and replaced by imputed values described in the next paragraph.

Imputation of missing data after treatment discontinuation

Missing LDL-C values during the post-treatment period will be imputed assuming LDL-C values would on average return to baseline values.

For each patient, missing post-treatment LDL-C values will be imputed 100 times, using a random draw from a normal distribution (SEED=9261), with mean equal to patient's own baseline value and variance equal to the conditional variance at the specific time-point, given the baseline value.

Let Y_0 and Y_1 denote the LDL-C at baseline and at the specific time-point respectively. Since Y_0 and Y_1 are assumed to have a bivariate normal distribution, the conditional variance of Y_1 given Y_0 is:

$$Var(Y_1|Y_0 = y_0) = \sigma_1^2(1 - \rho^2)$$

Where σ_1^2 denotes the variance of Y_1 and ρ the coefficient of correlation between Y_0 and Y_1 .

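### SAP Appendix 10.7 leaves region out of the multiple-imputation model, although the protocol's own rule calls for it and the analysis models use it

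*SAP*

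**What the plan says.** - **Stratification.** SAP Section 2.1: "The randomization will be stratified by apheresis treatment (Yes, No) and by region (Japan, Rest of World"). Protocol Section 10.1 says that these "will be the 2 stratification factors for patient randomization, and will be accounted for in the statistical modeling for efficacy". SAP Section 5.7.1 uses the term randomization strata for the two factors together.
- **Rule for imputation.** Protocol Section 10.4.3.2, for binary endpoints: "The variables in the multiple imputation model will at least include the same variables as used in the logistic regression model". For TG and Lp(a): "The variables in the multiple imputation model will at least include the same variables as used in the robust regression model". The adult protocol and the protocol for patients aged 12 and over carry the same wording.
- **Analysis models.** The robust regression in SAP Section 5.7.2.2 has "treatment group, randomization strata (as per IVRS/IWRS) and corresponding baseline value(s"). The logistic regression in Section 5.7.2.3 is "stratified by randomization strata defined as per IVRS/IWRS".
- **Imputation model.** In SAP Appendix 10.7, step 1 uses treatment and the repeated values only. Step 2 adds age, BMI, gender and "the randomization strata (apheresis treatment status strata"). Region is not named anywhere in the appendix.
- **Pattern-mixture model.** SAP Appendix 10.8: "The imputation model will include the treatment arm, baseline LDL-C value, and all LDL-C values at pre-specified visits". The sample code has the same list. The ANCOVA that follows includes the randomization strata.
- **Declared departures.** SAP Section 1.2.4 lists one change from the protocol, to the as-treated rule for the safety set. It does not mention imputation.

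**The concern.** The SAP departs, without saying so, from a rule that the protocol states outright, and it does so for endpoints inside the alpha-controlled hierarchy. A programmer who follows Appendix 10.7 literally would leave region out.

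An imputation model that lacks a variable used in the analysis draws missing values as if that variable carried no information beyond the other predictors. Imputed values for Japanese patients are then pulled toward those for the rest of the world, and the analysis model, which separates the two, sees a diluted difference. The treatment comparison could also shift if missingness differed by arm within region.

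**Working it through.** **1. Variable lists side by side**

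| Analysis | Analysis model | Imputation model | Absent from imputation |
|---|---|---|---|
| TG, Lp(a) (SAP 5.7.2.2) | arm, apheresis, region, baseline | 10.7 step 1: arm, baseline, visits. Step 2 adds apheresis, age, BMI, gender | region in both steps; apheresis in step 1 |
| Binary endpoints (SAP 5.7.2.3) | arm and baseline, stratified by apheresis and region | as above | as above |
| Pattern-mixture ANCOVA (SAP 10.8) | arm, apheresis, region, baseline | arm, baseline, visits | apheresis and region |

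**2. Endpoints reached.** SAP Section 4.7.2 lists nine key secondary endpoints in testing order. Five are binary and use Appendix 10.7: reduction of at least 30% (4th), at least 50% (5th), US apheresis criteria (7th), LDL-C below 100 mg/dL (8th) and EU apheresis criteria (9th). From Section 4.7.3, add TG, Lp(a) and LDL-C below 70 mg/dL. The primary MMRM has both strata and does no imputation.

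**3. Which step fills week 24.** Step 1 only makes the pattern monotone, so it fills gaps that are followed by a later observed value. Week 24 is the last planned time point. A missing week-24 value is therefore always left to step 2, where apheresis is present and region is not.

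**4. How many values.** The plan's sample size reproduces. With a two-sample t-test, difference 38, SD 35, two-sided 0.05 and 2:1 allocation, 14 + 28 = 42 patients give 89.9% power and 15 + 30 = 45 give 91.9%. So 45 are needed, and 45/(1 − 0.20) = 56.25, which rounds up to 57. Applying the same allowances (5% non-evaluable, 15% dropout) to the 57:

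- missing week-24 values: 57 × 0.20 = 11.4
- of these, Japanese, with 9 of 57 enrolled: 11.4 × 9/57 = 1.8

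Both are upper-end figures. They treat every allowed loss as a missing value and use the maximum Japanese enrolment.

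**5. Effect on estimates.** This is an illustrative simulation; its settings are assumptions, not document figures. It has 57 patients with 9 Japanese split 6:3, one continuous week-24 endpoint, a baseline covariate, residual SD 35, true treatment effect −38, 20% missing, 20 imputations and 1,500 runs.

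| Assumed region effect | Missingness | Region in imputer | Treatment estimate | Empirical SE | Combined SE | Region estimate |
|---|---|---|---|---|---|---|
| 0 | same for all | yes | −38.1 | 11.0 | 11.3 | 0.1 |
| 0 | same for all | no | −38.2 | 11.0 | 11.3 | 0.1 |
| 15 | same for all | yes | −38.0 | 11.5 | 11.2 | 14.6 |
| 15 | same for all | no | −38.0 | 11.5 | 11.3 | 11.5 |
| 30 | same for all | yes | −38.4 | 11.7 | 11.3 | 30.0 |
| 30 | same for all | no | −38.4 | 11.8 | 11.5 | 23.7 |
| 30 | +30 points in Japanese placebo | yes | −37.8 | 11.4 | 11.6 | 30.0 |
| 30 | +30 points in Japanese placebo | no | −36.2 | 11.5 | 11.9 | 21.0 |

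With equal missingness the region difference falls to about 0.79 of its value (11.5/14.6 and 23.7/30.0), close to the observed fraction of 0.80. The treatment estimate does not move.

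**6. Reach of the pattern-mixture omission.** Appendix 10.8 discards the model-based draws for values missing after treatment and redraws them around the patient's own baseline. A patient whose last dose is at week 16 or earlier leaves the on-treatment period by day 113 + 35 = 148, before the week-24 window opens on day 155. Adding strata to the imputation model cannot change that week-24 value. Only values missing on treatment are touched.

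**The case against.** The gloss in Appendix 10.7 may be a drafting slip, because the same appendix later refers to the randomization strata without qualification. That is plausible, but as written region is out, and a slip is a reason to correct the text.

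The practical effect is likely to be slight. Region is balanced between arms by stratified randomization. Step 2 already has treatment, baseline, earlier visits, apheresis, age, BMI and gender, so region matters only for what it adds to those. Patients who stop study drug stay in the study, and every effort is made to obtain week 24 (Protocol Section 7.4.2), so the real number missing may be well below 11. If one arm has no responders, LOCF with exact logistic regression replaces multiple imputation and the issue disappears. All of this stands and limits the size of the point. It does not remove the conflict with the protocol.

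A reader might infer that Appendix 10.8 breaks the same protocol rule. It does not. The rule is written for the imputation behind the robust and logistic regressions. For the pattern-mixture model, Protocol Section 10.4.3.1 asks only that imputation reflect the missing-value patterns on and off treatment. What remains is a mismatch with that model's own ANCOVA, in a sensitivity analysis.

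**Conclusion.** The point holds as an undeclared inconsistency between SAP Appendix 10.7 and the protocol. It reaches five of nine key secondary endpoints and three other secondary endpoints, and leaves the primary analysis alone. It is minor: at most about 11 imputed week-24 values, about 2 of them Japanese, under the assumptions in the working.

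Three stronger readings are tempting and not supported:

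- **That the treatment effect is biased or the standard errors unsound.** In the simulation the treatment estimate moved (−37.8 to −36.2) only with a 30-point region effect combined with 30 points more missingness in Japanese placebo patients; the documents give no ground for either. Combined and empirical standard errors agreed about as well without region as with it. The simulation used a continuous endpoint, so it is a guide to the responder endpoints and not a direct test of them.
- **That one or two responder classifications would change.** The figure of about 2 counts missing Japanese values. It does not count altered outcomes, and nothing in the documents converts one into the other.
- **That the pattern-mixture omission reaches every imputed patient on apheresis.** Only values missing on treatment are affected, and the documents do not say how many patients will be on apheresis.

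**What to change.** - **Appendix 10.7, step 2:** name the strata as apheresis and region, per IVRS/IWRS. This edit reaches the week-24 endpoints.
- **Appendix 10.7, step 1:** add both strata as 0/1 variables, or give a reason for leaving them out. Keep any list of minimum bounds aligned with the variables.
- **Appendix 10.8:** add both strata as 0/1 variables to the VAR statement. The MINIMUM list now has nine entries for nine variables, so add two '.' entries in the matching positions. If the strata follow ARM, the list becomes three '.' entries and then eight zeros, eleven in all. Without this the bounds would apply to the wrong variables.
- **Fallback:** state in advance what is done if the small Japan cells (6 and 3 patients at most, at 2:1) prevent estimation.
- **Alternative for 10.7:** keep the present model, and list and justify the departure in SAP Section 1.2.4.

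The cost is a few lines of text and code. Sample size, power, alpha and data collection do not change, and SAP Section 1 allows revision before the first-step database lock.

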10.8. Detailed Description of Pattern Mixture Model

As a sensitivity analysis of the primary efficacy endpoint (i.e. percent change from baseline to Week 24 in LDL-C), a pattern-mixture model approach will be used, with a different imputation strategy applied for missing LDL-C values during the on-treatment period (i.e. within the time period from the first double-blind study treatment administration up to the day of the last double-blind study treatment administration +35 days or to the day before the first open-label study treatment administration, whichever comes first) and missing LDL-C values after treatment discontinuation (i.e. after the day of last study treatment administration +35 days) based on the following assumptions:

- Patients within 35 days of their last study treatment administration would continue to show benefit from treatment similar to that observed at the scheduled time point. Therefore, LDL-C values missing during the on-treatment period will be considered “Missing at Random” and imputed using a model estimated using all samples collected on treatment.
- Patients who stopped taking their study treatment no longer benefited from it in the future, and thus tended to have LDL-C values returning to baseline. Thus LDL-C values missing after treatment discontinuation will be imputed based on patient’s own baseline value.

The assumptions for this approach are based on the following considerations:

- Missing values during the on-treatment period are mostly consecutive to:
 - Visits performed outside of the pre-specified time-window
 - No blood sample available although visit was done
 - LDL-C not measurable due to technical reasons

In addition, these missing data are often intermittent, i.e. followed by LDL-C values collected at subsequent visits. It is therefore considered reasonable to assume that these missing data were “At Random”.

Missing LDL-C values will be imputed 100 times to generate 100 complete data sets. The percent change from baseline to Week 24 will be derived from observed and imputed LDL-C at this time point. The completed data sets will be analyzed using an analysis of covariance (ANCOVA) model with treatment group and randomization strata as fixed effects, and the baseline LDL-C value as continuous covariate. The results from the 100 analyses will be combined using Rubin’s formulae. If necessary, the number of imputations (100) will be increased until stable estimates are obtained.

Imputation of missing data during the on-treatment period

Missing LDL-C values during the on-treatment period will be imputed from other on-treatment measurements assuming Missing At Random, using SAS® MI procedure.

Only LDL-C values collected during the on-treatment period will be included in the imputation model. This way, missing LDL-C values during the on-treatment period will be imputed based solely on observed on-treatment LDL-C values.

The imputation model will include the treatment arm, baseline LDL-C value, and all LDL-C values at pre-specified visits. Since the pattern of missing data will necessarily be non-monotone, a Monte-Carlo Markov Chain (MCMC) method will be used. A minimum value of 0 will be specified in order to avoid negative imputed LDL-C values.

A sample SAS code is provided below:

```
proc mi data=DATAIN out=DATAOUT nimpute=100 minimum=. 0 0 0 0 0 0 0 0 seed=1629;  
  mcmc impute=monotone;  
  var ARM LDL_BASE LDL_W2 LDL_W4 LDL_W8 LDL_W12 LDL_W16 LDL_W20  
  LDL_W24;  
run;
```

As stated above, the input dataset DATAIN will include only LDL-C values collected during the on-treatment period. Any LDL-C values collected during the post-treatment period will be excluded from the input dataset. In practice, the MI procedure will generate imputed values for all missing values (whether on-treatment or post-treatment), but only imputed values during the on-treatment period will be kept in the final datasets that will be analyzed using ANCOVA. Imputed values during the post-treatment period will be discarded and replaced by imputed values described in the next paragraph.

Imputation of missing data after treatment discontinuation

Missing LDL-C values during the post-treatment period will be imputed assuming LDL-C values would on average return to baseline values.

For each patient, missing post-treatment LDL-C values will be imputed 100 times, using a random draw from a normal distribution (SEED=9261), with mean equal to patient's own baseline value and variance equal to the conditional variance at the specific time-point, given the baseline value.

Let Y_0 and Y_1 denote the LDL-C at baseline and at the specific time-point respectively. Since Y_0 and Y_1 are assumed to have a bivariate normal distribution, the conditional variance of Y_1 given Y_0 is:

$$Var(Y_1|Y_0 = y_0) = \sigma_1^2(1 - \rho^2)$$

Where σ_1^2 denotes the variance of Y_1 and ρ the coefficient of correlation between Y_0 and Y_1 .

The conditional variance will be estimated from observed data within the same treatment arm at the specific time-point.

During the random generation process, a minimum value of 0 will also be applied in order to avoid negative imputed LDL-C values.

